KCE shall have the right (but not the obligation) to be present at each TSC meeting (more details can be found in the research agreement template).

The TSC will meet on average 3 times per year the first year and twice a year after that. The TSC is composed of the CI, the trial statistician, the trial PM, a representative of other participating centres or groups, up to 2 patients or members of the public, 1 representative of the sponsor, 1 representative of the funder.

The day-to-day management of the study will be performed by the Trial Management Group (TMG) which is distinct from the TSC and consists of the chief investigator and the trial coordinators.

TRIAL FLOW CHART

Figure 1 Flow chart ARON project

Figure 2 intervention arm: detailed flowchart

🖄 : decision tree, 🌢 : point-of-care CRP test, 🏊 : antibiotic treatment, 🦄 : safety netting advice, 🎹 : additional testing, H: referral to secondary care

Figure 2 describes the different steps of the diagnostic algorithm. First of all, the decision tree will be applied, if yes to any of three features (gut-feeling, dyspnea, temperature >40°C), physicians are advised to perform a point-of-care CRP test. If the CRP level is then 5 mg/L or above: referral or additional testing is advised to rule out a potential serious infection. If all features of the decision tree are reassuring (no to all) and a physician is still considering prescribing antibiotics, we advise them to perform a point-of-care CRP test and only consider prescribing if the CRP level is 5 mg/L or above. For example, in a child with dyspnee and a CRP level of <5mg/L, physicians are advised to prescribe antibiotics only if according to the prescribing guidelines.

Figure 3 control arm: detailed flowchart

. U: clinical assessment, ♥: clinical management, ♥: antibiotic treatment

(*) G	uidance on antibiotic prescribing (BAPCOC guide (November 2019) + RIZIV consensu	s meeting)
Preliminary diagnosis	Required criteria for rational antibiotics prescribing or referral	1 st choice AB treatmen
Bronchiolitis	Antibiotics: not indicated Referral: clinical deterioration; <3 months; breathing rate >60/'; reduced intake	none

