4.2.3. Re-consultation during follow-up

The third secondary outcome is re-consultation with their physician during follow-up (day 1 to day 30).

Null hypothesis: the diagnostic algorithm including a standardised clinical assessment, a POC CRP test and safety netting advice is inferior to usual care in terms of the proportion of subjects re-consulted their physician during followup from day 1 to day 30

Alternative hypothesis: the diagnostic algorithm including a standardised clinical assessment, a POC CRP test and safety netting advice is not inferior to usual care in terms of the proportion of subjects re-consulted their physician during follow-up from day 1 to day 30

- P Children aged 6 months to 12 years of age with an acute illness episode presenting to in-hours general practices or community paediatrics offices
- I Diagnostic algorithm including a standardised clinical assessment, a POC CRP test and safety netting advice
- C Diagnosis and treatment/management as per usual care
- O Re-consultation during follow-up from day 1 to day 30
- T This outcome will be checked from the patient health record from day 1 to day 30 after the index consultation
- 4.2.4. Antibiotic prescribing rate during follow-up

The fourth secondary outcome is antibiotic prescribing rate during follow-up (day 1 to day 30).

Null hypothesis: the diagnostic algorithm including a standardised clinical assessment, a POC CRP test and safety netting advice is inferior to usual care in terms of the proportion of subjects receiving a prescription for immediate or delayed antibiotic treatment during follow-up from day 1 to day 30 compared to usual care

Alternative hypothesis: the diagnostic algorithm including a standardised clinical assessment, a POC CRP test and safety netting advice is not inferior to usual care in terms of the proportion of subjects receiving a prescription for immediate or delayed antibiotic treatment during follow-up from day 1 to day 30 compared to usual care

- P Children aged 6 months to 12 years of age with an acute illness episode presenting to in-hours general practices or community paediatrics offices
- I **Diagnostic algorithm** including a standardised clinical assessment, a POC CRP test and safety netting advice
- C Diagnosis and treatment/management as per usual care
- O Antibiotic prescribing rate during follow-up from day 1 to day 30
- T This outcome will be checked from the patient health record from day 1 to day 30 after the index consultation

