Follow-up information for all children will be collected from the patient health record up to 30 days after the index consultation. This information will be collected by the participating GP (follow-up form in the eCRF will be due 30 days after the index consultation) with or without support of a flying nurse during on-site visits after blocks of patients included. Follow-up information will consist of: diagnosis of a serious infection, re-attendance visits, medication prescribed, use of additional tests, admission to hospital, death, prioritizing the data related to safety events (mortality, admission to hospital, detection of a serious infection) as these would need to be assessed first in the eCRF, allowing appropriate safety measures to be put in place.

Interviews as part of the nested qualitative study

Individual telephone interviews will be conducted with a small selection of clinicians (approximately 16) and a selection of parents (approximately 14 to 18) taking part in the trial (nested qualitative study), to explore the social processes influencing embedding of the intervention within practice, and behaviour change techniques.

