(1) R Core Team (2023). R: A language and environment for statistical computing. R Foundation for Statistical Computing, Vienna, Austria. URL https://www.R-project.org/.

(2) Posit team (2023). RStudio: Integrated Development Environment for R. Posit Software, PBC, Boston, MA. URL http://www.posit.co/.

(3) Douglas Bates, Martin Maechler, Ben Bolker, Steve Walker (2015). Fitting Linear Mixed-Effects Models Using lme4. Journal of Statistical Software, 67(1), 1-48. doi:10.18637/jss.v067.i01.

(4) Rotondi MA (2023). _CRTSize: Sample Size Estimation Functions for Cluster Randomized Trials_. R package version 1.2, <https://CRAN.R-project.org/package=CRTSize>

Interim analyses

No interim analyses are planned.

Data Source

Our study utilized a prospective data collection approach, drawing from several sub-databases to create a comprehensive dataset for analysis:

1. **REDCap Database.** A secure web application for building and managing online surveys and databases. REDCap was utilized for its robust data capture capabilities, particularly for complex longitudinal data and multisite clinical research studies.

2. ARON App Database. A user-centred database collected through direct patient/parent contact via a mobile application over a 30-day follow-up period. These data encompass information on daily symptoms, healthcare consultations, hospital visits, and health-related quality of life (HRQoL).

3. Administrative Database (healthcare utilization). Data obtained from the Intermutualistische Agentschap (IMA) on potential hospitalizations, technical provisions, and reimbursed pharmaceutical usage up to 3 months post-index consultation. Access to this administrative data for ARON participants is enabled by a secure procedure developed to transmit national insurance numbers in compliance with GDPR regulations, facilitated by a trusted third party. This data is collected for all ARON trial participants with valid national insurance numbers.

4. Interview Transcripts. A process evaluation is nested within the ARON trial, aiming to gather insights into the utilization and perceptions of the intervention by physicians and (parents of the) patients. This qualitative process evaluation entails conducting individual semi-structured, in-depth interviews with GPs and parents, facilitated through video conferencing.

Date of final version of dataset

1. REDCap Data

Estimated date of receipt 29/03/2024.

2. ARON App Data

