Drop-outs are unlikely to be a large problem since there will be only one study visit complemented by the collection of follow-up information.

We will analyse the whole population for the primary analysis and perform a sensitivity analysis excluding the low recruiting practices (less than 10 patients recruited for 12 months) to avoid our results to be susceptible to selection bias. In previous trials this resulted in approximately 10% of practices.

Practices that do not recruit children at all will be stopped after the first two monitoring visits and replaced by new practices to avoid reducing the total number of clusters available for analysis.

The percentage of missing data for the primary outcome of antibiotic prescribing proportion is expected to be low as this will be registered at the first contact consultation. In our previous ERNIE2 trial, we found 4% of missing data for the primary outcome of antibiotic prescribing proportion. Multiple imputation will be considered for the primary outcome measure as well as missing values for patient-reported outcomes (if there are any). Other outcomes will be collected from the patient health record of the physician.

Multiple imputation will be applied to deal with missing data. Imputation will be performed for the binary outcome variable and logistic regression will be used as imputation model. Predictors for the imputation model are baseline patient characteristics and intervention.

2. ARON App Data

A substantial drop-out rate in app completion is anticipated, with non-completion of the app not considered grounds for exclusion from the study. To address this, proactive measures were introduced to enhance participation rates, such as the provision of information about the smartphone app and instructions on installation to children and their parents during the baseline consultation. Additionally, the app was made available in three languages (Dutch, French, English).

Multiple imputation will be applied to deal with missing data. For imputation of continuous variables, a linear regression model will be employed, with baseline patient characteristics and intervention serving as predictors for the imputation model.

3. Administrative Data

Multiple imputation, following Rubin's rules, will be utilized to address missing data. Predictors for the imputation model will include baseline patient characteristics and the intervention.

4. Interview Transcripts

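### Follow-up antibiotics and admissions rest on the recruiting physician's record, and the linked insurer data already being obtained are not used to check how complete that record is in each arm

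*Protocol*

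**What the plan says.** **Source.** Protocol 4.2.4 defines the fourth secondary outcome, antibiotic prescribing during follow-up, and gives its source: "This outcome will be checked from the patient health record from day 1 to day 30 after the index consultation". Protocol 8.7 puts medication, re-attendance, tests, admissions and deaths on the same footing: "Follow-up information for all children will be collected from the patient health record up to 30 days after the index consultation". On who does this it says: "This information will be collected by the participating GP (follow-up form in the eCRF will be due 30 days after the index consultation". A visiting nurse may help. Physicians are not masked (Protocol 8.2). The SAP, under handling of missing values for the REDCap data, agrees: "Other outcomes will be collected from the patient health record of the physician".

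**Care elsewhere.** Children are enrolled in in-hours general practices or community paediatric offices. In the intervention arm, for a child positive on the decision tree with CRP of 5 mg/L or above, the text under Figure 2 of the Protocol says "referral or additional testing is advised to rule out a potential serious infection".

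**Other data.** The parent app asks daily about treatment, consultations and hospital visits (Protocol 8.7), but it is named as the source only for time to recovery (Protocol 4.2.1), and the SAP expects a substantial share of families to stop completing it. The SAP's Data Source section also lists "Data obtained from the Intermutualistische Agentschap (IMA) on potential hospitalizations, technical provisions, and reimbursed pharmaceutical usage up to 3 months post-index consultation", for every participant with a valid national insurance number. Protocol 11.4 describes that linkage for the economic evaluation. The SAP gives the insurer data no role in secondary outcome 4 or the admission endpoints. It schedules the primary and secondary analyses for April to June 2024, and the economic analysis, which depends on IMA delivery, for January to February 2025.

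**The concern.** Protocol 4.1 says any fall in index prescribing must be weighed against the secondary outcomes, follow-up antibiotics among them. That outcome therefore helps to carry the claim that prescribing is reduced safely.

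An antibiotic from an out-of-hours service, an emergency department, a hospital or another doctor counts only if it has reached the recruiting physician's record when the form is completed. Protocol 11.4 itself recognises the gap: it uses the app for resources that the health records do not capture, and combines app and linkage to avoid missing data. That safeguard is given to the economic evaluation and not to the clinical endpoints.

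The two endpoints are affected differently. Follow-up antibiotics are judged against a 2-point absolute margin, so missed events can change a non-inferiority conclusion. Admissions are exploratory with no margin (Protocol 4.5), so what is at stake there is a safety count that may be too low.

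**Working it through.** **1. The plan's own figure.** Inputs from Protocol 11.1.1 for outcome 4: intervention 7%, usual care 8%, margin 2 points, power 0.80, alpha 0.05, design effect 2.225. With a non-inferiority formula for two proportions and unpooled variance:

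- Distance to the margin: 0.02 − (0.07 − 0.08) = 0.03
- Variance term: 0.07 × 0.93 + 0.08 × 0.92 = 0.1387
- n per arm = (1.645 + 0.842)² × 0.1387 / 0.03² = 953, so 1906 in total
- 1906 × 2.225 = 4241, against 4240 stated

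The figure reproduces at one-sided 0.05. The stated decision rule, upper limit of the 95% confidence interval below the margin, is one-sided 0.025 if that interval is two-sided. It then needs 1210 per arm, 2420 in total, and 2420 × 2.225 = 5385, still below 7000. Power at 7% versus 8% with 7000 children is about 89%. Sample size is not the issue here.

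**2. What incomplete capture does to the rule.** Put the true rates on the margin: 8% usual care, 10% intervention. Multiply each by an assumed share c of prescriptions that reaches the record. With 3500 children per arm:

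- Recorded difference d = 0.10 × c_I − 0.08 × c_C
- SE = √{2.225 × [p_C(1 − p_C) + p_I(1 − p_I)] / 3500}, using the recorded rates
- P(declare non-inferiority) = Φ[(0.02 − d)/SE − 1.96]

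Worked case, capture 80% in both arms: recorded rates 6.4% and 8.0%, d = 1.6 points, SE = √[2.225 × (0.0599 + 0.0736)/3500] = 0.0092, and Φ(0.004/0.0092 − 1.96) = 6.4%.

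| Assumed capture, control / intervention | Recorded difference (points) | Chance of wrongly declaring non-inferiority |
|---|---|---|
| 100% / 100% | 2.0 | 2.5% |
| 90% / 90% | 1.8 | 4.0% |
| 80% / 80% | 1.6 | 6.4% |
| 95% / 90% | 1.4 | 8.9% |
| 90% / 80% | 0.8 | 24.5% |
| 90% / 95% | 2.3 | 1.2% |
| 80% / 90% | 2.6 | 0.5% |

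Equal loss raises the error modestly. Loss concentrated in the intervention arm raises it sharply. Loss concentrated in usual care lowers it. Every capture share is an assumption, because the documents give none.

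**3. The scale matters.** The SAP reports odds ratios and states no margin on that scale. There, equal 80% capture hardly moves the effect: (0.10/0.90)/(0.08/0.92) = 1.278 becomes (0.08/0.92)/(0.064/0.936) = 1.272. The equal-loss result above therefore applies to the protocol's absolute rule. Unequal loss distorts either scale.

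**4. The window.** Protocol 4.2.4 counts from day 1. Protocol 4.4 and the SAP endpoint list count from immediately after the index consultation. An antibiotic given elsewhere later on the index day is inside the second window and outside the first, so a cross-check must choose one.

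**The case against.** The strongest reply is that the record does not stand alone and that the insurer data measure something else.

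- The proportion of children who actually took antibiotics from day 0 to day 30 is a listed exploratory endpoint, not limited by prescriber. The app asks about treatment and hospital visits. The SAP's cost-consequences analysis will compare hospitalisations and pharmaceuticals between arms. Protocol 8.10.4 asks for every effort to obtain follow-up when care is transferred, and admissions are prioritised and monitored monthly (Protocol 8.7 and section 10). All this is true and lowers the risk. None of it reconciles the sources for secondary outcome 4 or for the clinical admission endpoints, and no source is named for antibiotics actually taken.
- IMA holds reimbursed dispensing, whereas the outcome is prescribing, immediate or delayed. An unfilled delayed prescription will not appear, and an index prescription filled late will look like a new event. This stands. It makes IMA a cross-check and not a replacement, and the check needs a rule for late fills.

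A reader might infer more: that because the algorithm advises referral or testing in one branch, events are lost mainly in the intervention arm and the trial leans towards non-inferiority. By Protocol 11.1.1 that branch holds 0.17 × 0.72 = 12.2% of children. If 25% were seen elsewhere, 47% of those treated there and none recorded, 0.1224 × 0.25 × 0.47 = 1.4 points would be hidden. That figure leaves out the control arm. Applying the same 25% to all tree-positive children in usual care, with the protocol's guideline shares of 47% and 24%, hides 0.17 × 0.25 × (0.72 × 0.47 + 0.28 × 0.24) = 1.7 points. If no intervention child with CRP below 5 mg/L is referred, the sign reverses. The shares are also guideline advice at the index contact, not follow-up treatment rates; testing need not leave the practice; and complete non-arrival of letters is extreme. Usual care works under guidance that lists referral criteria for nearly every diagnosis, and the Protocol background expects a CRP below 5 mg/L to avoid some referrals. The documents do not support a direction.

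**Conclusion.** The point holds in a limited form. The recruiting physician's record is the only named source for follow-up antibiotics and admissions, it is read by an unmasked physician, and the documents do not say how often outside care reaches it. For follow-up antibiotics this can shift the comparison with the 2-point margin either way. In the assumed scenarios the chance of a wrong declaration ranges from 0.5% to 24.5%, against 2.5% with full capture. Those figures rest on true rates of 8% and 10%, 7000 children, design effect 2.225, an upper 95% limit on the absolute scale, and invented capture shares. They show sensitivity and do not estimate the bias.

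For admissions the conclusion is only that events may be under-counted; no non-inferiority claim is involved. A reader might also infer that the outcome 4 conclusion should be held back until the insurer data arrive. The documents do not require that, and it is a matter of preference. Because direction and size are unknown, agreement between sources should be measured in each arm. This is a cheap improvement and does not show the planned analysis to be invalid.

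**What to change.** In the SAP:

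1. State the source for each follow-up endpoint and keep the eCRF analysis as the main one.
2. Pre-specify a sensitivity analysis of follow-up antibiotics and of admissions in which an event counts if it is in the eCRF or in the IMA data (a reimbursed antibacterial dispensed, or a hospitalisation). Run it from immediately after the index consultation to day 30, to match Protocol 4.4.
3. Exclude dispensings that fill an index prescription by a stated rule: for example, the first dispensing of the same antibacterial in a child with an index prescription in the eCRF. Protocol 8.7 lists only whether the index antibiotic was prescribed and whether it was immediate or delayed, so the SAP should say what applies if the substance is not recorded.
4. Report eCRF-versus-IMA agreement by arm, and interpret the outcome 4 non-inferiority result alongside it.

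The cost is SAP wording and one further analysis of data already being linked. The drawbacks are that it waits for the IMA delivery, covers only children with a valid national insurance number, and measures reimbursed dispensing rather than prescribing.

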4.3 Primary endpoint

The primary outcome is the proportion of subjects who were prescribed antibiotic treatment (both immediate and delayed) at the index consultation as recorded by the treating physician.

4.4 Secondary endpoints

- the duration (in days) until reaching full clinical recovery
- the proportion of subjects receiving additional testing (including, but not limited to (X-Ray, blood tests, urine tests) at index consultation (day 0) and/or during follow-up (day 1 to day 30)
- the proportion of subjects who re-consulted their physician during follow-up (day 0 to day 30)
- the proportion of subjects who were prescribed antibiotic treatment during follow-up (immediately after index consultation to day 30)

4.5 Exploratory endpoints

- the proportion of subjects receiving additional testing (including, but not limited to (X-Ray, blood tests, urine tests) at index consultation (day 0)
- the proportion of subjects receiving additional testing (including, but not limited to (X-Ray, blood tests, urine tests) during follow-up (day 1 to day 30)
- the proportion of subjects referred to hospital at index consultation (day 0)
- the proportion of subjects referred to hospital during follow-up (day 1 to day 30)
- the proportion of subjects admitted to hospital at index consultation (day 0)
- the proportion of subjects admitted to hospital during follow-up (day 1 to day 30)
- the proportion of subjects who died at index consultation (day 0)

- the proportion of subjects who died during follow-up (day 1 to day 30)
- the proportion of subjects with full clinical recovery at day 7
- the proportion of subjects with full clinical recovery at day 30
- Patient's satisfaction (as part of the nested qualitative study)
- Parent's satisfaction (as part of the nested qualitative study)
- Physician's satisfaction (as part of the nested qualitative study)
- Cost-effectiveness of the intervention: healthcare expenditures in terms of hospitalization, consultations, pharmaceuticals (reimbursed and non-reimbursed), productivity, quality of life
- Adherence to the diagnostic algorithm
- the proportion of subjects who actually took antibiotics (from day 0 to Day 30)

5 TRIAL DESIGN

This study is a pragmatic cluster randomised controlled superiority trial:

multicentre:	6 academic centres for primary care will be involved in the recruitment of 122 primary care practices
pragmatic:	criteria excluding patients from participation will be limited as well as procedures that do not reflect care as usual
cluster:	randomisation occurs at the level of the primary care practice while patients are the unit of analysis
randomised:	block randomization per academic centre will be performed to assign primary care practices to either the intervention or the control arm
controlled:	the intervention will be compared with usual care
superiority:	the trial is designed to show that the intervention is superior to usual care

The rationale for choosing a cluster design is to prevent contamination across the intervention and control arm. The cluster and unit of randomization is the physician's practice. There will be 2 arms - the intervention arm and the usual care arm - in 50:50 ratio.

